## 11 General Specifications for Statistical Analyses

Unless otherwise indicated all analyses will be presented separately for the two treatment groups under different food condition (fed and fasted).

#### Listings

All listings will be reported separately by food condition and sorted by treatment, or treatment sequence (A-B or B-A), and/or scheduled timepoint, as appropriate. Data which are only measured before administration of trial drug and/or at end of study will be sorted by subject and scheduled timepoint (if appropriate).

All PK concentrations will be reported and analyzed with the same precision as the source data provided by the bioanalytical laboratory or clinical laboratory regardless of how many significant figures or decimal places the data carry. Pharmacokinetic parameters and actual elapsed sample collection times will be rounded for reporting purposes in by-subject listings. Actual elapsed sample collection times will be rounded to two decimal places with units of hours. For PK parameters, the standard rounding procedure will be as follows:

- Parameters directly derived from source data (e.g.,  $C_{max}$ ) will be reported and analyzed with the same precision as the source data.
- Parameters derived from actual elapsed sample collection times [e.g., time to reach maximum observed plasma concentration  $(t_{max})$ ] will be reported to two decimal places with units of hours.
- Values of AUC will be rounded to 3 significant figures.
- Percentages not derived directly from source data [e.g., percentage of area under the plasma concentration-time curve from time zero to infinity (AUC0-∞) obtained by extrapolation (AUCextra%)] will be reported to 3 significant figures.
- Other parameters [e.g., apparent terminal half-life  $(t_{1/2})$ , terminal elimination rate constant  $(\lambda_Z)$ , apparent total body clearance of drug from plasma following extravascular administration (CL/f), apparent volume of distribution during the terminal phase following extravascular administration  $(V_{Z/f})$ ] will be reported with 3 significant figures.

#### **Tables and Descriptive Statistics**

All data will be summarized by food condition, treatment, or treatment sequence, and/or scheduled time point, as appropriate. Repeated and unscheduled measurements included in the listings will not be used for statistical analyses or summaries, unless the repeated measurement was performed due to unreliable values/technical reasons, e.g., clotted samples.

Bisoprolol and amlodipine concentrations in plasma, and their PK parameters, will be presented in tables and descriptively summarized by food condition, treatment, and/or nominal time point, as appropriate.

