3.2 Bisoprolol

Bisoprolol is a potent, highly synthetic β_1 -selective (cardioselective) adrenoceptor blocking agent without significant membrane stabilizing activity or intrinsic sympathomimetic activity in its therapeutic dosage range. This preferential effect is not absolute, however, and at higher doses bisoprolol may also inhibit β_2 -adrenoceptors, located chiefly in the bronchial and vascular musculature. Bisoprolol is a racemic mixture and the S (-) enantiomer is responsible for most of the β -blocking activity. It may be used alone or in combination with other antihypertensive agents. It is indicated for the management of hypertension and angina pectoris.

As with other β_1 -blocking agents, the mode of action in hypertension is not clear but it is known that bisoprolol markedly depresses plasma renin levels. Factors which may be involved include: antagonism of β -adrenoceptors to decreased cardiac output, inhibition of renin release by the kidneys, and diminution of tonic sympathetic outflow from the vasomotor centers in the brain. In normal volunteers, bisoprolol therapy resulted in a reduction of exercise and isoproterenol-inducted tachycardia. The maximal effect occurred within 1 to 4 hours postdose. Effects persisted for 24 hours at doses equal to or greater than 5 mg.

Bisoprolol is well absorbed following oral administration. The absolute bioavailability after a 10 mg dose is greater than 80%. Absorption is not affected by the presence of food. The first pass metabolism of bisoprolol is less than 20%. Binding to serum proteins is approximately 30%. Peak plasma concentrations occur within 2 to 4 hours of dosing with 5 to 20 mg, and mean peak values range from 16 ng/mL after a 5 mg dose to 70 ng/mL after a 20 mg dose. Once daily dosing with bisoprolol results in less than a 2-fold inter-subject variation in peak plasma levels. The plasma elimination $t_{1/2}$ is 10 to 12 hours and is slightly longer in elderly patients in part because of decreased renal function in that population. Steady-state is attained within 5 days with once-daily dosing. In both young and elderly populations, plasma accumulation is low; the accumulation factor ranges from 1.1 to 1.3, and is what would be expected from the first order kinetics and once-daily dosing. Plasma concentrations are proportional to administered dose in the range of 5 to 20 mg. Pharmacokinetic (PK) characteristics of the 2 enantiomers are similar.

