Electrocardiogram Recording

A 12-lead ECG (including QTc evaluation) will be performed.

Results of the ECG recordings will be included in the subject's eCRF. Printouts for each ECG will include date, time, initials of the technician/nurse, and initials of the Investigator who reviewed the printout. At least 5 to 7 beats will be monitored at a speed of 25 mm/sec for each lead and a single lead (V2) run (see Section 7.3.4 for specific ECG determinations and procedures).

Chest X-ray

A chest X-ray examination will be performed.

Laboratory Tests

Hematology assessments

Parameter	Dimension/Unit
Erythrocytes	×10 ¹² /L
Hemoglobin	g/L
Hematocrit	%
Mean corpuscular volume	fL
Mean corpuscular hemoglobin	pg
Mean corpuscular hemoglobin concentration	g/L
Red blood cell distribution width	%
Platelets	×10 ⁹ /L
Mean platelet volume	fL
Thrombocytocrit	%
Platelet distribution width	%
White blood cells	×10 ⁹ /L

Hematology assessments for differential white blood cell counts

Parameter	Dimension/Unit
Neutrophils	10 ⁹ /L and %
Monocytes	10 ⁹ /L and %
Lymphocytes	10 ⁹ /L and %

Biochemistry assessments

Parameter	Dimension/Unit
Alanine aminotransferase	IU/L
Aspartate aminotransferase	IU/L
Total bilirubin	μmol/L
Direct bilirubin	μmol/L
Indirect bilirubin	μmol/L
Protein total	g/L
Albumin	g/L
Globulin	g/L
A/G	(Not applicable)
Alkaline phosphatase	IU/L
Glutamyl transpeptidase	IU/L
Urea nitrogen	mmol/L
Creatinine	μmol/L
Cholesterol	mmol/L
Triglycerides	mmol/L
Glucose	mmol/L
Creatine kinase	IU/L
Lactate dehydrogenase	IU/L
Calcium	mmol/L
Phosphorus	mmol/L
α-Amylase	U/L
Sodium	mmol/L
Potassium	mmol/L
Chloride	mmol/L

Note: If creatine kinase is above the upper limit of normal and evaluated as clinically relevant, a retest should be done and the creatine phosphokinase MB isoenzyme should be determined.

Urinalysis

Appearance, blood, glucose, ketones, nitrite, pH, protein, and leukocytes will be assessed. Microscopic examination will only be performed if dipstick test is positive for leukocytes, blood, nitrites, or proteins.

Serum pregnancy test

Pregnancy testing for females of childbearing potential only (Human Chorionic Gonadotropin in serum)

Other laboratory tests

Serology

HIV antibody

HBsAg

HCV antibody

TP antibody

Urine screening of drugs of abuse

The following urine tests for drug abuse will be conducted: levels for other drugs of abuse (eg, cannabis, benzodiazepines, barbiturates, opiates, cocaine, and methyl amphetamine).

Breath test of alcohol

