Details of the assay may differ from above and will be provided in the Analytical plan separately.

The complete schedule for each trial period is presented in Table 3. The clock time of all blood draws will be recorded and reported for each subject in the eCRF. The actual sampling times, if available, will always be used for calculation.

Table 3 Sampling Collection Schedule

Trial Day	Period Day	Time of Blood Sample (hour)	Window Allowance (minute)
1	1 – Predose in Period 1	Baseline blood draw (10 minutes prior to drug administration)	±2
1	1 – Single dose administration and Washout begins	0.5, 1, 1.5, 2, 3, 4, 6, 8, 10, 12, 15	±2
2	2	24, 36	±5
3	3	48	±5
4	4	72	±30
5	5	96	±30
6	6	120	±30
7	7	144	±30
8	8	168	±30
9 - 14			
15	1-Predose in Period 2	Baseline blood draw (10 minutes prior to drug administration)	±2
15	1- Single dose administration and Washout begins	0.5, 1, 1.5, 2, 3, 4, 6, 8, 10, 12, 15	±2
16	2	24, 36	±5
17	3	48	±5
18	4	72	±30
19	5	96	±30
20	6	120	±30
21	7	144	±30
22	8	168	±30
23 - 28			
End of Trial (Day 29)/Premature Withdrawal		1-sample	±30

Safety Monitoring

Vital signs (blood pressure, pulse rate, temperature and respiration) will be repeated prior to dosing and at 4, 8, and 12 hours postdose.

A 12-lead ECG (including QTc evaluation) will be performed 4 hours postdose.

Any concomitant diseases and treatments should be documented. Any AEs and SAEs should also be recorded.

Concurrent administration of any medication will be prohibited during the trial (Section 6.5.1).

Day 2 to Day 8, Period 1

Pharmacokinetic Blood Sampling (Postdose, continued)

During the 7 days following Day 1, blood samples will be taken according to the trial schedule (Table 3). On Day 2, sampling will be conducted at 24 and 36 hours; from Day 4 to Day 8, sampling will be conducted every 24 hours. Subjects will be allowed to leave the CRU on Day 8 after the morning blood sampling collection (168-hour sample).

Safety Monitoring

Any concomitant diseases and treatments have to be documented. Concurrent administration of any medication will be prohibited during the trial. Any AEs and SAEs should also be recorded.

Vital signs (blood pressure, pulse rate, temperature and respiration) will be assessed before blood sampling from Day 2 to Day 8.

A 12-lead ECG (including QTc evaluation) will be performed 48 hours postdose at Day 3.

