7.3.5 Vital Signs, Physical Examinations, and Other Assessments

Safety and tolerability will be assessed by monitoring of vital signs (blood pressure, pulse rate, temperature and respiration) and physical examinations.

Despite the fact that bisoprolol and amlodipine are usually safe and well tolerated, one cannot fully exclude the possibility of an incidence of bradycardia or hypotension.

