## 17.3 Vital Signs

The following parameters will be measured during the trial as safety evaluation:

Blood Pressure	Pulse rate	Temperature	Respiration Rate	

Markedly abnormality of vital signs will be identified in accordance with the criteria as follows:

Vital Sign Parameter	Unit	Low	High
Systolic blood pressure	mmHg	< 85 mmHg	> 139 mmHg
Diastolic blood pressure	mmHg	< 50 mmHg	> 90 mmHg
Pulse rate	Beats/min	< 50 Beats/min	> 100 Beats/min
Temperature	 C	< 36 °C	> 37.3 °C

Systolic and diastolic blood pressures (mmHg), pulse rate (beats/min) measurements in supine position as well as body temperature (°C) and respiration (breaths/min) will be presented by descriptive statistics overall and by treatment sequence for each group at screening and end of study visit, and by group, treatment and time point for the values obtained during the treatment periods as raw data and change from baseline.

Baseline is Period 1 Day 1 pre-dose (or Day-1 if missing at Day 1 pre-dose) for Period 1 and End of study visit and Period 2 Day 1 pre-dose for Period 2. All data will be listed by group, treatment sequence, subject, treatment, visit, and time point.

All marked abnormal for vital signs values will be listed. Vital signs variables will be summarized in frequency tables based on a classification by treatment.

All data will be listed by group, treatment sequence, subject, treatment, visit, and time point.

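### SAP 11 keeps off-schedule blood pressure and pulse readings out of the SAP 17.3 frequency table by treatment, so a low value not reported as an AE is listed but never counted

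*SAP*

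**What the plan says.** **The general rule.** SAP 11, under Tables and Descriptive Statistics, states: "Repeated and unscheduled measurements included in the listings will not be used for statistical analyses or summaries". The same sentence has one exception: "unless the repeated measurement was performed due to unreliable values/technical reasons, e.g., clotted samples". The rule stands in a paragraph about the summary of all data, so it covers safety data as well as PK data.

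**Vital signs.** SAP 17.3 introduces a grid of Low and High limits: "Markedly abnormality of vital signs will be identified in accordance with the criteria as follows". The low limits are 85 mmHg systolic, 50 mmHg diastolic and 50 beats/min. Values beyond the limits go into a listing. SAP 17.3 then adds: "Vital signs variables will be summarized in frequency tables based on a classification by treatment". It does not say which classification is meant, or whether unscheduled readings count.

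**Schedule and expected risk.** Protocol 7.1.3 (Safety Monitoring) says: "Vital signs (blood pressure, pulse rate, temperature and respiration) will be repeated prior to dosing and at 4, 8, and 12 hours postdose". Protocol 3.2 says of bisoprolol in volunteers: "The maximal effect occurred within 1 to 4 hours postdose". Protocol 7.3.5 accepts that "one cannot fully exclude the possibility of an incidence of bradycardia or hypotension".

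**Laboratory values.** SAP 17.2 plans low/normal/high frequency tables against reference ranges, and shift tables by time point. It includes CK-MB among the biochemistry parameters, all of which are to be summarised. Protocol 7.1.1 has no CK-MB in the standard panel. If creatine kinase is high and clinically relevant, "a retest should be done and the creatine phosphokinase MB isoenzyme should be determined".

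**The concern.** Leaving unscheduled readings out of means by time point is normal practice, because they belong to no nominal time. A count of subjects with an out-of-limit value is different. The SAP 17.3 frequency table is specified by treatment and not by time point, so alignment to nominal times gives no reason to drop readings from it. Off-schedule readings are often taken because something has been noticed, and they are the ones such a table should not lose.

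What is at stake is the completeness of one descriptive comparison. Examining the safety and tolerability of the combination tablet against the separate tablets is a secondary objective (Protocol 4.2). Under the rule as written, a low reading taken off schedule can be visible in a listing and absent from every count by treatment.

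**Working it through.** No arithmetic applies, and the plan gives no figure to reproduce. The check is whether any other provision brings an excluded reading back into a count.

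1. **Scope of the rule.** The SAP 11 exception covers repeats made for unreliable values or technical reasons. It does not cover an unscheduled reading, or a repeat prompted by a clinical finding.
2. **Override.** SAP 17.2, 17.3 and 17.4 contain no sentence that restores such readings to a summary.
3. **Which vital-sign output is affected.** The listing of marked abnormalities is not affected, because SAP 11 restricts analyses and summaries only. The frequency table is. The Low/High grid is the only classification in SAP 17.3, so the natural reading is that the table counts values against those limits. The SAP does not say so.
4. **Where off-schedule readings can fall.** Dosing-day vital signs are due predose and at 4, 8 and 12 h. Any reading after dosing and before 4 h is therefore unscheduled, as is any reading between the later times.
5. **The AE route.** Under Protocol 7.3.1.1 an abnormal investigational finding is not reported as an AE unless it comes with signs or symptoms, leads to discontinuation, or is otherwise judged medically important. I take vital signs to fall under that rule. SAP 17.1.1 tabulates treatment-emergent AEs by treatment within each cohort.

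Applied to cases, taking the table to use the Low limits:

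| Reading | Listed | Frequency table by treatment | AE table by treatment |
|---|---|---|---|
| Scheduled 4 h pulse below 50, no symptoms, not judged important | Yes | Counted | No |
| Unscheduled 2 h pulse below 50, no symptoms, not judged important | Yes | **Not counted** | No |
| Unscheduled 2 h systolic below 85 with symptoms | Yes | Not counted | Counted |
| Scheduled pulse below 50, normal on a clinically prompted repeat | Yes | Counted (scheduled value) | No, unless an AE |
| Scheduled pulse within limits, below 50 on a clinically prompted repeat | Yes | **Not counted** | No, unless an AE |

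The second row, and the fifth when no AE is reported, are the gap.

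6. **Laboratory tables.** The shift tables are by time point, so restricting them to scheduled values is reasonable. The low/normal/high frequency table is not clearly tied to time points, and where it is not, the same question arises. CK-MB has no scheduled determination. If a reflex CK-MB counts as unscheduled, SAP 11 removes every value that SAP 17.2 says will be summarised. The SAP does not say whether it does.

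**The case against.** **The important events are already counted.** Symptomatic hypotension or bradycardia is an AE and is tabulated by treatment, with event counts and subject percentages. This stands, and it confines the point to readings that are off schedule and not reported as AEs. A reader might infer that bradycardia and hypotension found off schedule vanish from all safety tables. The AE tables and the complete listings rule that out.

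**Repeats need not cause undercounting.** A reader might infer that excluding repeats generally lowers the abnormality counts. It does not. An abnormal scheduled value that prompts a repeat stays in the table, and what is dropped is the repeat, which may be normal. Only a repeat that is itself newly out of limits is lost.

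**The 1 to 4 h argument is limited.** The protocol's statement on maximal effect follows a sentence on exercise- and isoproterenol-induced tachycardia, not resting values. The 4 h reading lies at the edge of that window, and the 8 and 12 h readings fall in amlodipine's 6 to 12 h peak. The lack of a reading before 4 h belongs to the protocol schedule and was not caused by SAP 11. This stands too. The window is an example of where an uncounted reading could fall, not evidence that one will.

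**A magnitude is tempting.** With 16 subjects per cohort, one subject is 1/16 = 6.25 percentage points of a cell. That is the weight of any one subject, not an estimate of how many would be missed.

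**Scheduled-only counts are even-handed.** In an open-label trial, discretionary readings could be taken more often under one treatment, and a table that includes them could reflect that. This is a fair objection, and it is the reason to show both counts. It does not justify having no count of the off-schedule values.

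**CK-MB.** Calling a reflex test unscheduled is an inference. A clarification is all it warrants.

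**Conclusion.** The point holds in a limited form. SAP 11 excludes unscheduled readings and non-technical repeats from all summaries, and SAP 17.3 does not override this for its frequency table by treatment. An out-of-limit blood pressure or pulse found off schedule and not reported as an AE would therefore be listed but not counted.

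The size cannot be given as a number. The documents do not say how many off-schedule readings to expect or how many would be out of limits, and the effect is nil if there are none. The consequence is confined to descriptive safety counts; the PK analysis and the bioequivalence decision are not affected. The documents do not support saying that the counts by treatment will be wrong, only that they can be incomplete.

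The conclusion rests on two assumptions: that the unnamed classification in SAP 17.3 is its own Low/High grid, and that abnormal vital signs follow the protocol's AE rule for abnormal investigational findings. The change is worth making because it is cheap and serves a stated secondary objective.

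**What to change.** - **SAP 11:** limit the exclusion of unscheduled and repeated measurements to by-time-point descriptive statistics and by-time-point shift tables. Keep the technical-repeat exception.
- **SAP 17.3:** state that the frequency table uses the marked-abnormality Low and High limits. Classify each subject once per treatment as low if any post-dose value in that period meets the low limit, and as high if any meets the high limit, including unscheduled and repeat readings. Show scheduled-only counts alongside. Counting each subject once also settles the unit, since SAP 17 speaks of counts of observations while SAP 11 bases proportions on subjects. State the period window, and treat the Day 15 predose reading as the Period 2 baseline, as SAP 17.3 already does.
- **SAP 17.2:** apply the same any-post-dose rule to the low/normal/high frequency table where it is not by time point. State that reflex CK-MB results are reported despite the general exclusion.

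The cost is a few sentences and minor programming, with no new data. Abnormality counts may rise slightly. Discretionary readings may be ascertained unequally between treatments, which the scheduled-only counts make visible. The change belongs before database lock. After lock the table can still be produced, identified as unplanned under SAP 5.

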#### **Presentation of PK Concentration Data**

Pharmacokinetic concentration data will be descriptively summarized using: number of non-missing observations (N), arithmetic mean (Mean), standard deviation (SD), standard error of the mean (SEM), coefficient of variation (CV%), minimum (Min), median (Median) and maximum (Max).

Descriptive statistics of PK concentration data will be calculated using values with the same precision as the source data, and rounded for reporting purposes only. The following conventions will be applied when reporting descriptive statistics of PK concentration data:

Mean, Min, Median, Max: 3 significant digits

SD: 4 significant digits

CV%: 1 decimal place

Derived parameters will be reported using precision similar to the precision of the data from which they were derived.

Descriptive statistics of plasma concentration will additionally show quartiles, and values below the lower limit of quantification (LLOQ) will be taken as zero.

#### **Presentation of PK Parameter Data**

Pharmacokinetic parameter data will be descriptively summarized using: number of non-missing observations (N), Mean, SD, CV%, Min, Median, Max, geometric mean (GeoMean), the geometric coefficient of variation (GeoCV%), and the 95% confidence interval (CI) for the GeoMean (LCI 95% GM, UCI 95% GM).

Pharmacokinetic parameter  $C_{max}$  will be reported with the same precision as the source data and  $t_{max}$  will be reported to two decimal places. All other PK parameters will be reported to 3 significant figures. In export datasets, as well as in the Study Data Tabulation Model (SDTM) PP/XD domain, PK parameters will be provided with full precision, and will not be rounded. Descriptive statistics of PK parameter data will be calculated using full precision values, and rounded for reporting purposes only.

The following conventions will be applied when reporting descriptive statistics of PK parameter data:

Mean, Min, Median, Max, GeoMean, 95% CI: 3 significant digits

SD: 4 significant digits

CV%, GeoCV%:

1 decimal place

To ensure a reliable estimate of the extent of exposure in pivotal trials (e.g., bioequivalence), AUCextra% should be less than or equal to 20.0%. If AUCextra% is greater than 20.0%, all parameters derived using  $\lambda_z$  (i.e.,  $\lambda_z$ ,  $t_{1/2}$ , AUC0-\infty AUCextra%,  $V_z/f$ , and CL/f) will not be included in the calculation of descriptive statistics or statistical analyses.

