3.1 Amlodipine

Amlodipine is a calcium ion influx inhibitor of the dihydropyridine group (slow channel blocker or calcium ion antagonist) and inhibits the transmembrane influx of calcium ions into cardiac and vascular smooth muscle. It is indicated for the treatment of hypertension and for prophylaxis of chronic stable angina pectoris.

The therapeutic effect of this group of drugs is believed to be related to their specific cellular action of selectively inhibiting transmembrane influx of calcium ions into vascular smooth muscle and cardiac muscle, with a greater effect on vascular smooth muscle cells than on cardiac muscle cells.

The mechanism of the antihypertensive action of amlodipine is due to a direct relaxant effect on vascular smooth muscle. The precise mechanism by which amlodipine relieves angina has not been fully determined, but it reduces total ischemic burden by the following 2 actions: it dilates peripheral arterioles and thus reduces the total peripheral resistance (afterload) against which the heart works. Since the heart rate remains stable, this reduced load on the heart consequently reduces myocardial energy consumption and oxygen requirements. It also probably involves dilation of the main coronary arteries and coronary arterioles, both in normal and ischemic regions. This dilation increases myocardial oxygen delivery in patients with coronary artery spasm (Prinzmetal's or variant angina).

The recommended initial dose is 5 mg once daily and can be increased after 1 to 2 weeks to a maximum dose of 10 mg once daily.

After oral administration of therapeutic doses of amlodipine, absorption occurs gradually with peak plasma concentration reached between 6 and 12 hours. Absolute bioavailability has been estimated to be between 64% and 90%. The absorption of amlodipine is not altered by the presence of food. Amlodipine is metabolized through the cytochrome P450 (CYP) system, mainly via CYP 3A4 isoenzyme.

Amlodipine is extensively (about 90%) converted to inactive metabolites (via hepatic metabolism) with 10% of the parent compound and 60% of the metabolites excreted in the urine. Ex vivo studies have shown that approximately 93% of the circulating drug is bound to plasma proteins in hypertensive patients. Elimination from the plasma is biphasic with a terminal elimination half-life $(t_{1/2})$ of about 35 to 50 hours. Steady state plasma levels of amlodipine are reached after 7 to 8 days of consecutive daily dosing.

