## 16.2 Secondary Endpoint Analyses

All secondary PK endpoints will be descriptively summarized as described in Section 11. The secondary PK endpoints are the following parameters in plasma for bisoprolol and amlodipine:

•  $t_{max}$ ,  $t_{1/2}$ ,  $\lambda_Z$ ,  $AUC_{0-\infty}$ ,  $AUC_{extra}$ %, CL/f,  $V_{z/f}$ .

For  $t_{max}$ , the Hodges-Lehmann estimates for the treatment differences and corresponding 90% CIs according to the Tukey method will be calculated.

The mixed-effects model for treatment comparison as described for the primary endpoints will also be applied to  $AUC_{0-\infty}$ . The ratios of geometric means and corresponding 90% CIs for Treatment A/Treatment B will be estimated.

All secondary endpoints ( $t_{max}$ ,  $t_{1/2}$ ,  $\lambda_Z$ ,  $AUC_{0-\infty}$ ,  $AUC_{extra\%}$ , CL/f, and  $V_{z/f}$ ) will be summarized descriptively by group and treatment on the PK analysis set.

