The Rsq should be  $\geq$ 0.800 and the observation period over which the regression line is estimated should be at least two-fold the resulting  $t_{1/2}$  itself. If these criteria are not met, then the rate constants and all derived parameters (e.g.,  $AUC_{0-\infty}$ ,  $AUC_{extra}$ %, CL/f,  $t_{1/2}$ , and  $V_{z/f}$ .) will be included in the parameter outputs and descriptive statistics but will be flagged and discussed appropriately. Any flags should be included in the study specific SDTM.

For both analytes, if more than 20% of  $AUC_{0-\infty}$  is extrapolated ( $AUC_{extra}\% > 20.0\%$ ), then  $AUC_{0-\infty}$  and  $\lambda_Z$  estimates and parameters derived from them (e.g.,  $CL_f$ ) will be calculated and included in the listing, but flagged as unreliable and set to missing in summaries and in inferential statistical analysis.

The dose amount for investigational medicinal product (IMP) administered is that of the active, free drug substance only, and is synonymous with the measured analyte. No adjustment for the dose amount value of IMP will be applied when 'dose' is used in calculating PK parameters with formulas needing a dose value.

The Phoenix WinNonlin NCA Core Output will be provided in a separate listing.

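### The 20% extrapolation rule removes AUCextra% from its own summary, so its tabulated maximum cannot exceed 20.0%, and it trims the longest amlodipine half-lives

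*SAP*

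**What the plan says.** AUCextra%, λz and t1/2 are secondary endpoints. SAP Section 16.2 states that all of them "will be summarized descriptively by group and treatment on the PK analysis set". SAP Section 11 (Presentation of PK Parameter Data) fixes the statistics for PK parameters, beginning with "number of non-missing observations (N), Mean, SD, CV%, Min, Median, Max". No count of profiles above 20% is planned.

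Section 11 also sets 20.0% as the upper limit of extrapolation for a reliable estimate of exposure. If AUCextra% "is greater than 20.0%, all parameters derived using" λz are dropped. The list given is λz, t1/2, AUC0-∞, AUCextra%, Vz/f and CL/f, and these "will not be included in the calculation of descriptive statistics or statistical analyses".

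Section 16.3.2 states the rule again for both analytes. It names AUC0-∞, λz and whatever is derived from them; these "will be calculated and included in the listing, but flagged as unreliable and set to missing in summaries", and are also missing from inferential analysis.

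The same section handles a poorly determined λz differently. If Rsq is below 0.800, or the regression interval is shorter than twice the resulting t1/2, the rate constant and its derived parameters "will be included in the parameter outputs and descriptive statistics but will be flagged and discussed appropriately".

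**The concern.** AUCextra% tells the reader whether sampling ran long enough. A summary of it should be able to show failure. Here a value is deleted from the summary exactly when it fails, so the mean is pulled down and the maximum is capped at the acceptance limit by construction.

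The rule's stated purpose, a reliable estimate of the extent of exposure, is a reason to guard AUC0-∞ and what is computed from it. It is not a reason to withhold the diagnostic. The handling is also uneven. A half-life from a poor regression stays in the summary with a flag, while a long half-life from a good regression is removed.

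With a fixed last sample, AUCextra% rises with t1/2. The exclusion therefore takes half-lives from the upper end only, and any distortion of summarized t1/2 is downward.

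**Working it through.** The plan gives no figure for the effect of this rule, so there is none to reproduce.

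**Inputs from the documents.** Amlodipine terminal half-life "of about 35 to 50 hours" and peak at 6 to 12 h (Protocol 3.1). Bisoprolol half-life 10 to 12 h, peak at 2 to 4 h, mean Cmax 16 ng/mL after 5 mg (Protocol 3.2). Last sample in each period at 168 h and expected bisoprolol lower limit 0.500 ng/mL (Protocol 7.1.3).

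**Assumption.** The documents give no between-subject CV for half-life. I take a lognormal distribution with CV 25% and then vary the CV from 20% to 40%.

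**Step 1: the cap on AUCextra%.** No model is needed. Values above 20.0% are missing from the summary, so the largest value left is at most 20.0%.

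**Step 2: the half-life at which amlodipine is cut.** Ignoring the absorption phase, AUCextra% ≈ 100 × 2^(−168/t1/2).
- t1/2 = 35 h: 2^(−4.80) = 3.6%.
- t1/2 = 50 h: 2^(−3.36) = 9.7%.
- AUCextra% = 20%: t1/2 = 168 × ln 2 / ln 5 = 72.4 h.

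With an absorption phase that peaks at 6 to 12 h, the cut moves only to 71.8 to 70.9 h. A typical amlodipine profile is well below the limit; the rule acts on the upper tail.

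**Step 3: effect on the summaries at CV 25%.** Let m be the median, s = √ln(1 + 0.25²) = 0.246 and z = ln(72.4/m)/s. The proportion cut is p = 1 − Φ(z). The mean of all half-lives is m·exp(s²/2). The mean of those kept is m·exp(s²/2)·Φ(z − s)/Φ(z). The chance of at least one subject cut in a cohort of 16 is 1 − (1 − p)^16.

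| Median t1/2 | z | Cut | At least one in 16 | Mean t1/2, all → kept | Change |
|---|---|---|---|---|---|
| 35 h | 2.95 | 0.2% | 2.5% | 36.1 → 36.0 h | −0.2% |
| 42.5 h | 2.16 | 1.5% | 22% | 43.8 → 43.3 h | −1.3% |
| 50 h | 1.50 | 6.7% | 67% | 51.5 → 49.4 h | −4.1% |

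At a median of 50 h, averaging the step 2 formula over the same distribution gives a mean AUCextra% of 10.6% for all profiles and 9.7% for those kept. The 99th percentile, 26.9%, would not appear in the table.

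**Step 4: sensitivity to the assumed CV.** A simulation with an absorption phase (peak at 8 h) gave these changes in mean t1/2:

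| Median t1/2 | CV 20% | CV 30% | CV 40% |
|---|---|---|---|
| 35 h | 0 | −0.9% | −4.1% |
| 42 h | −0.3% | −3.1% | −8.4% |
| 50 h | −1.9% | −7.4% | −14.3% |

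**Step 5: bisoprolol.** With the protocol's half-life, Cmax and lower limit, the last quantifiable scheduled sample falls at 48 h and AUCextra% is about 4 to 7%. Exclusion is unlikely.

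**The case against.** **The exclusions are not hidden.** A reader might infer that the report will show adequate coverage whatever the data say. The documents do not support that. Excluded values are still calculated, listed and flagged, the WinNonlin core output is listed separately, and N is reported, so a shortfall against the PK Analysis Set is visible. This stands. But a reduced N shows neither the reason nor the size of what was removed, and the summary itself stays capped.

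**Washout is not judged from the half-life table.** A reader might also infer that the trimmed t1/2 hides an inadequate washout, because Protocol 6.3 cites a guideline of 7 half-lives and 14 days (336 h) covers that only up to 336/7 = 48 h. But the SAP checks carry-over through the predose concentration: above 5% of Cmax, the profile is treated as affected (SAP 10.2 and 16.3.2). No rule uses summarized t1/2 for this. The objection stands, and I make no claim about washout.

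**The removed half-lives are poorly estimated.** At 72 h, the SAP's wish for a regression interval of twice t1/2 needs 144 h of a 168 h profile, so the regression must start by 24 h. This partly stands: the removed values are less certain, and the true bias is less certain too. Yet Section 16.3.2 flags and keeps profiles that fail that very criterion, so uncertainty alone does not explain their removal.

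**Unpaired periods.** The rule can remove one period of a subject from the AUC0-∞ analysis. The mixed model has a random subject effect and accepts this, and no harm can be shown from the documents.

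**Conclusion.** The truncation of AUCextra% is certain and needs no assumption: both statements of the rule lead to it, and the tabulated maximum cannot exceed 20.0%.

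The effect on half-life is conditional. It arises only if at least one profile exceeds 20%, it concerns amlodipine, and it is usually small: about 0 to −4% in the mean for medians of 35 to 50 h at CV 25%. The largest figure, −14%, needs both the top of the protocol's half-life range as the median and a CV of 40%. These sizes rest on an assumed CV and a one-compartment approximation. Biphasic disposition would change the percentages somewhat, but not the direction. A flat statement that half-life is biased low would go too far.

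Bioequivalence is decided on AUC0-t and Cmax, which do not use λz, so the primary conclusion is unaffected. This is a flaw in the reporting of secondary endpoints, and worth correcting because the correction is cheap.

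**What to change.** In SAP Sections 11 and 16.3.2:
- Summarize AUCextra% for all profiles in the PK Analysis Set, with those above 20% flagged.
- Report the number and percent of profiles above 20% by analyte, treatment and food cohort.
- Show t1/2 and λz with and without the flagged profiles, in line with the flag-and-keep handling that Section 16.3.2 already applies to the Rsq and regression-interval criteria.
- The exclusion may stay for AUC0-∞, CL/f and Vz/f. A repeat of the AUC0-∞ model with all profiles is optional.

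The cost is a change of wording in two places and a few table rows. The values are already to be calculated and listed, so no new data or derivations are needed.
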